13. NEW FINDINGS

Subjects will be informed of any significant new findings related to study products or procedures when they become known during the course of this clinical research study. Such information may affect the subject's decision to continue participation in the study.

14. STATISTICAL ANALYSIS AND SAMPLE SIZE

14.1. Statistical Analysis

14.1.1. Descriptive Analyses

Descriptive summaries of baseline and longitudinal data will include the number of observations, mean, standard deviation (SD), median, and range for continuous variables. Categorical data will be summarized using the number of observations and percentages.

Descriptive analyses will be performed for the overall enrolled study population as well as for subgroups defined by comorbid disease category and assigned treatment group.

14.1.2. Primary Analyses

Analyses associated with the first primary outcome, the impact of treatment on oral health measures, will be performed using generalized estimating equations (GEE) methods. Longitudinal outcomes in the Treated vs. Control groups will be compared and will include all subjects who were randomized and their data from visits T1 - T4 based on intent-to-treat (ITT) group assignment.

The second primary outcome, association between changes in oral health and changes in systemic health, will be evaluated using correlation analysis. Changes in the measures of oral and systemic health between Baseline (T0) and follow-up visit 4 (T4) will be calculated for all subjects in the study who complete the T4 visit. The strength of correlations between changes in oral health and change in HbA_{1c} (in subjects with prediabetes or type 2 diabetes) or change in flow mediated dilation will be evaluated.

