1.2. Outcomes

Primary

- Impact of non-surgical periodontal treatment on oral health as measured by changes in periodontal probing depths
- Correlations between changes in periodontal health and changes in systemic health measures:
 - Glycated hemoglobin (HbA1c) (prediabetic and type 2 diabetic cohorts)
 - Flow-mediated dilation

Secondary

- Impact of treatment on other oral health measures:
 - Bleeding on probing
 - Clinical attachment level
 - Dental plaque index
 - Gingival index
- Impact of treatment on systemic health measures:
 - Flow-mediated dilation
 - Glycated hemoglobin (HbA1c) (prediabetic and type 2 diabetic cohorts)
 - Carotid intima media thickness (IMT)
 - High sensitivity C-reactive protein (hs-CRP) (all cohorts)
 - Lipid profile: Total cholesterol/LDL cholesterol/Triglycerides
- Impact of treatment on emotional (affectional) state and beliefs about disease as measured by PANAS and PMT surveys

Exploratory

- Prevalence and severity of periodontal disease in screen-eligible participants at initial oral health screening
- Relationship between treatment on all other molecular analytes, including protein, metabolite and immune system inflammatory biomarkers and subgingival plaque microbiome
- Correlations among all other oral and systemic health metrics
- Correlations among oral and systemic health metrics with molecular analytes, including inflammatory biomarkers and subgingival plaque microbiome.

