At the Baseline visit, another oral health assessment will be conducted, along with collection of biospecimen samples ie. blood, stool (optional), saliva, plaque, tongue biofilm, and gingival crevicular fluid. Subjects will then be randomized using a 1:1 protocol to a standard care group (Control Group) and a therapy group (Treatment Group). The Control Group will receive an initial periodontal treatment consisting of a pre-procedural rinse and scaling & root planing (SRP). Subjects in the Control group should refrain from non-study periodontal treatments for the duration of the study. The Treatment Group will receive the same periodontal treatment in addition to having subgingival chlorhexidine irrigation. All subjects will also complete a set of questionnaires (PANAS & PMT) using an online form. A subset of 50 subjects from each group will be randomly selected to have oral images captured using an intra-oral scanner at Baseline and a subset of follow-up visits. Subjects in the Treatment Group will receive a commercial connected toothbrush, a stannous fluoride toothpaste , mouthwash , proxabrush , and floss to be used at home along with instructions on their use. Brush heads for the connected toothbrush will be replaced every 3 months and products (toothpaste, mouthwash, proxabrush, and floss) will be replenished at every site visit. Additionally, subjects in the

Treatment Group will also receive brief behavioral advice from dental professionals focusing mainly on motivation and acknowledgement. Subjects in the Control Group will receive no products during the course of the study. They will receive Colgate products which may include a commercial connected toothbrush, toothpaste, mouthwash, proxabrush, and floss at the end of the study.

For a subgroup of 50 individuals, levels of active matrix metalloproteinase-8 (aMMP-8) will also be measured quantitatively using rapid point of care (PoC) chairside aMMP-8 kits (Periosafe®, Dentognostics GmbH, Solingen, Germany). The additional samples will be collected from 4 sites on a tooth with probing depth $\geq 5\text{mm}$ on the same visit as GCF samples will be collected.

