Subjects will be scheduled to receive flow mediated dilation (FMD) and carotid intima media thickness (IMT) measurements prior to Baseline and approximately 8 weeks after their Baseline visit. Also in those visits, for a subset of 50 individuals aMMP8 activity will be measured using rinse method following manufacturer instructions and the chair side data positive aMMP-8 test is based on a cutoff of 25 ng aMMP-8 per milliliter of filtrate derived from 5 mL mouthrinse

Subjects in both the Control and Treatment Group will attend 3 follow-up visits (respectively T1-T3, see Figure 1). At these visits, the Control Group will have a clinical exam and a biospecimen collection while the Treatment Group will have a biospecimen collection followed by a clinical exam, periodontal treatment consisting of scaling and root planing and chlorhexidine preprocedural rinse and chlorhexidine irrigation (Chlorhexidine Gluconate Oral Rinse, 0.12%), and will be provided with new products to support the oral hygiene regimen. Finally, during follow-up visits, subjects in the Treatment Group will also receive specific behavioral advice focusing on monitoring their progress (through use of brushing data), motivation and reinforcement. Depending on the progress of each subject, IF-THEN plans designed to overcome barriers in using the oral hygiene regimen can be deployed. Dental professionals will be providing scripted and standardized advice to subjects to the Treatment Group. All subjects (control and therapy group) will also complete a set of questionnaires (PANAS & PMT) using an online form. FMD and IMT will also be measured (approximately 8 weeks after T2).

A fourth follow-up visit, (T4, see Figure 1) occurs at approximately Month 12 and at this visit, all subjects (regardless of group assignment) will receive a clinical exam, biospecimen collection, and periodontal treatment including subgingival chlorhexidine irrigation. At this visit, the treatment group will receive brief behavioral advice focusing on motivation and support and both groups will complete a set of questionnaires (PANAS & PMT) using an online form.

Participants will be scheduled to receive FMD and IMT measurements approximately 8 weeks after their T4 visit.

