3.2. Visit Schedule

| Visit | Screening (S0) | Screening Visit 1-2 ¹ (S1-S2) | Baseline (T0) | Follow-up 1 (T1) | Follow-up 2 (T2) | Follow-up 3 (T3) | Follow-up 4 (T4) | Follow-up 5 (Final visit) (T5) |
|---------------------------|----------------|--|---------------|-------------------|--------------------|--------------------|--------------------|--------------------------------|
| Timeline | -90 days | -89 to -14 days | 0 day | 90 days ± 28 days | 180 days ± 28 days | 270 days ± 28 days | 360 days ± 28 days | 450 day ± 28 days |
| Type of visit | Dental Clinic | Dental Clinic | Dental Clinic | Dental Clinic | Dental Clinic | Dental Clinic | Dental Clinic | Dental Clinic |
| Informed Consent | x | | | | | | | |
| Dental Screen | x | | | | | | | |
| Extractions ² | | x ² | | | | | | |
| Vitals | x | x | x | x | x | x | x | x |
| Medical History | x | x | x | x | x | x | x | x |
| Diet Questionnaire | | | x | x | x | x | x | x |
| PANAS | | | X (online) | X (online) | X (online) | X (online) | X (online) | X (online) |
| PMT | | | X (online) | X (online) | X (online) | X (online) | X (online) | X (online) |
| X-Ray Full Mouth Series | x | | | | | | | x |
| PreProcedural Rinse | | | x | x* | x* | x* | x | |
| Periodontal Exam | x | | x | x | x | x | x | x |
| Dental CRFs | x | x | x | x | x | x | x | x |
| Biological Samples: Blood | x*** | | x | x | x | x | x | x |

| | | | | | | | | |
|---|---|--|-----|----|-----|----|-----|-----|
| Biological Samples: GCF, [POC aMMP8 (subset)], saliva, plaque, tongue biofilm | | | x | x | x | x | x | x |
| Stool samples (optional) | | | x | | x | | x | |
| POC aMMP8 mouthrinse | | | x | | x | | x | |
| Carotid IMT Ultrasound | x | | x | | x | | x | |
| Flow- Mediated Dilation | x | | x | | x | | x | |
| Periodontal treatment | | | x | x* | x* | x* | x | |
| Intra-oral Scan (select subset) | | | x** | | x** | | x** | x** |
| Behavioral support (on site) | | | x* | x* | x* | x* | x* | |
| Review Brushing Data from Connected Brush | | | x* | x* | x* | x* | x* | x* |
| Distribute at-home regimen | | | x* | x* | x* | x* | x* | x |

¹Screening Visit (1-2) can span two days depending on the allotted time for extractions

²Extractions will occur as needed based on dental assessment

*Treatment group only

**For approximately 50 subjects from each of Control and Treatment groups

*** Blood sample - finger prick

Additional assessments would be conducted in addition to the above listed Schedule of Assessments. This may include:

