8. PROTOCOL APPROVAL, STUDY MONITORING AND COMPLIANCE

Institutional Review Board

The clinical investigation, including the consent form, will be reviewed by an Institutional Review Board in accordance with Title 21 of the Code of Federal Regulations, Parts 50 and 56. Approval by the Board must be obtained prior to the initiation of the study.

The study will be conducted in compliance with Good Clinical Practice Regulations, the study protocol and protocol amendment(s). Designated personnel will audit this study to ensure protocol compliance. In addition, study data and the Final Report will be examined for completeness, accuracy and proper documentation.

Informed Consent and Other Written Information for Subjects

The informed consent form and any other written information for subjects should meet local requirements of language and interpretation. One copy of the signed informed consent form and any other written information will be given to the subject or legal representative and the original will be retained by the investigator in the study files. The informed consent form and any other written information prepared by the investigator must be reviewed and approved by the sponsor and by the Institutional Review Board prior to their implementation. The informed consent form must include all required elements in accordance with GCP guidelines.

Protocol Compliance

The investigator is obligated to follow the provisions and requirements of the study protocol accordingly. Any changes to the protocol must be implemented only through formal written protocol amendments and only upon joint approval by the sponsor and investigator. All protocol amendments must be reviewed and approved prior to implementation by the institutional review board. If a protocol amendment requires changes to the informed consent form, the revised consent form must also be approved by the sponsor and the IRB.

Departures from eligibility requirements may be allowed on a case-by-case basis by the medical monitor or other authorized sponsor representative. Such departures must be medically and scientifically justified, must be pre-authorized, and must be documented in the case report form and tracked as official eligibility waivers.

Study Monitoring

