14.2. Sample Size and Power

This study is powered to detect a mean reduction in periodontal probing depth of 0.88 (SD 0.5) mm over the course of 12 months of periodontal therapy in the Treated group, versus a mean reduction of 0.63 (SD 0.59) mm in the Control group. Assuming a 2-tailed test with $\alpha = 0.05$, we need 200 subjects (100 per group) to have 90% power to achieve statistical significance. Assuming a 10% drop out during the study, this means we need to recruit approximately 200 - 224 subjects (112 per Control and Treatment group). If the dropout rate is found to be greater than 10%, additional recruitment may be required to achieve the target of approximately 100 - 112 per group.

For the correlation analyses, we can assume various distributions of prediabetes, type 2 diabetes, and cardiovascular disease among the study cohort (note that subjects may qualify for more than one category). Given the total sample size of 224, the table below describes the effect sizes (i.e., Pearson correlation coefficients) this study would have the power to detect with various cohort distributions and power levels.

Correlations able to be detected in a subgroup, by sample size and power

| | Cohort representation, out of overall study population, N = 224 | | | |
|-------|---|-------------|-------------|--------------|
| Power | 1/6, N = 37 | 1/4, N = 56 | 1/3, N = 75 | 1/2, N = 112 |
| 70% | 0.422 | 0.346 | 0.300 | 0.247 |
| 80% | 0.468 | 0.386 | 0.336 | 0.277 |
| 90% | 0.528 | 0.439 | 0.384 | 0.317 |

Note: $\alpha = 0.0$

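### The primary GEE should state its response and primary contrast and adjust for T0 probing depth; the 90% power claim stands, and the adjustment adds modest precision from data already collected

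*Combined protocol and SAP*

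**What the plan says.** Section 14.1.2 assigns the first primary outcome to GEE. The comparison of the arms "will include all subjects who were randomized and their data from visits T1 - T4 based on intent-to-treat (ITT) group assignment". The paragraph does not define the response (PD or change from T0). It names no T0 covariate, visit term, arm-by-visit term or primary visit. The next paragraph of the same section does name T0-to-T4 change, but only for the correlation outcome.

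Section 1.2 gives the outcome as "Impact of non-surgical periodontal treatment on oral health as measured by changes in periodontal probing depths". Section 14.2 states: "This study is powered to detect a mean reduction in periodontal probing depth of 0.88 (SD 0.5) mm over the course of 12 months", against 0.63 mm (SD 0.59) in Control. It asks for 100 per group for 90% power at two-sided 0.05. With 10% dropout, "this means we need to recruit approximately 200 - 224 subjects".

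On availability of T0 PD, Section 1.3 says "At the Baseline visit, another oral health assessment will be conducted" and places randomization after it. The Periodontal Exam row of the Section 3.2 table is marked at T0 and at every follow-up visit, with no restriction by group. T4 falls at about month 12, when "all subjects (regardless of group assignment) will receive a clinical exam, biospecimen collection, and periodontal treatment including subgingival chlorhexidine irrigation".

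**The concern.** The trial is sized on one quantity, the difference in 12-month reduction, and the analysis section does not name that quantity. As written, one analyst could model raw PD and another change in PD. One could test the T4 difference and another an average over T1-T4. These choices differ in precision and, for the last pair, in what is estimated.

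The text also makes no stated use of a pre-randomization measurement of the outcome itself. Used as a covariate, it would tighten the primary comparison without any new data. The stake is efficiency and prespecification. Neither bias nor a power shortfall is at issue.

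**Working it through.** **Inputs.** From Section 14.2: difference 0.88 - 0.63 = 0.25 mm, SDs of reduction 0.5 and 0.59, two-sided 0.05, 100 per arm. Assumed, because the documents do not give them: the T0-T4 correlation r, the ratio k = SD(T0)/SD(T4), and one PD value per subject (Section 2.2 records six sites per tooth, and Section 14.1.2 does not give the unit of analysis).

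**Step 1: reproduce Section 14.2.** Take V = 0.5² + 0.59² = 0.5981 and SE = √(V/n).
- At n = 100, SE = 0.0773 and 0.25/0.0773 = 3.23. Noncentral-t power is 89.6% (89.8% by the normal approximation).
- For 90% power, n is 102 per arm (101 by the normal approximation), against 100 stated.
- 100/0.9 gives 112 per arm, or 224 in total.

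The stated figures reproduce as a two-sample comparison of T0-to-T4 change.

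**Step 2: adjust the T4 contrast for T0 PD.** With a T4-specific slope on T0 PD, in large samples:
- adjusted / change score variance = (1 - r²)/(1 + k² - 2rk). The denominator equals (1 - r²) + (k - r)², so the ratio never exceeds 1, and it equals 1 only when k = r;
- adjusted / raw T4 PD variance = 1 - r², which also never exceeds 1.

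With equal SDs (k = 1) the first ratio is (1 + r)/2. Power then follows from SE² = V(1 + r)/(2n):

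| Assumed r | Variance ratio to change score | SE, n = 100 | Power, n = 100 | n per arm for 90% |
|---|---|---|---|---|
| change score | 1 | 0.0773 | 89.6% | 102 |
| 0.5 | 0.75 | 0.0670 | 96.0% | 77 |
| 0.7 | 0.85 | 0.0713 | 93.7% | 87 |
| 0.8 | 0.90 | 0.0734 | 92.4% | 92 |
| 0.9 | 0.95 | 0.0754 | 91.0% | 97 |

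If 200 are recruited and 10% drop out, 90 per arm remain. The change score then gives 86.2%, and adjustment gives 94.1% at r = 0.5 and 87.9% at r = 0.9.

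With unequal SDs at 100 per arm, k = 0.8 and r = 0.8 gives no gain (89.6%), while k = 1.25 and r = 0.8 gives 98.0%.

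**Step 3: why a T0 PD-by-visit term is needed.** A single T0 slope b shared by all visits gives a T4 variance of 1 - r² + (b - r)² (equal SDs, in units of σ²). Suppose T0 correlates 0.5 with T1-T3 and 0.8 with T4.
- b = (3 × 0.5 + 0.8)/4 = 0.575.
- Variance = 0.36 + 0.051 = 0.411, against 2(1 - 0.8) = 0.400 for the change score.

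The shared slope is slightly worse here. A visit-specific slope removes the (b - r)² term.

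**Step 4: T4 or the T1-T4 average.** Assume equal SDs and a common correlation r among all visits. The variance of an unadjusted T1-T4 average is (1 + 3r)/4, and that of the adjusted T4 value is 1 - r².
- r = 0.5: 0.625 against 0.75.
- r = 0.7: 0.775 against 0.51.
- They cross where 4r² + 3r - 3 = 0, near r = 0.57.

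If both are adjusted, the average has variance (1 + 3r)/4 - r², which is 0.285 at r = 0.7. It may also carry a smaller effect: if the difference grew linearly to 0.25 mm, its average would be 0.25 × (1 + 2 + 3 + 4)/16 = 0.156 mm. The documents give no visit profile, so neither contrast can be called the more powerful.

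**The case against.** The strongest reply is that T0 is not left out. Sections 1.2 and 14.2 speak of change and reduction, which need T0, and a GEE on change from T0 at each of T1-T4 fits the text of Section 14.1.2. A randomized comparison of change is valid, and the 90% claim holds under it. Adjustment is then an optimization of unknown size. This largely stands: the text is silent on how T0 enters and does not exclude it.

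A reader might infer that baseline is discarded and the trial underpowered. With raw T4 PD as the response and equal SDs, the variance relative to the change score is 1/(2(1 - r)), and power at 100 per arm is 70.3% at r = 0.7 and 53.0% at r = 0.8. The documents do not support that reading, because they define the outcome as a change. Those figures show only what the ambiguity would allow.

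A reader might also infer that any T0 covariate must help. Step 3 shows that a shared slope carries no such guarantee, although the counterexample is a marked departure. Nor does naming T4 in itself buy precision (Step 4).

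Finally, Sections 2.6 and 14.1.4 refer to a Statistical Analysis Plan, for randomization and exploratory details. A fuller primary model might be there, but no text available for review defers the primary model to it.

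**Conclusion.** The point holds as a worthwhile improvement and clarification. Section 14.1.2 leaves the response, the use of T0 PD and the primary contrast unstated. The sample size arithmetic is sound and N need not change.

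For the T4 difference, adjustment with visit-specific T0 slopes is in large samples no less precise than either alternative, whatever r and k are. Against the change score, the fair comparator, the gain at 100 per arm is 6.4 points of power at r = 0.5, 4.1 at 0.7, 2.8 at 0.8 and 1.4 at 0.9. It is nil when k = r. The size rests on assumed correlations, equal SDs in the main table and one PD value per subject. The choice between T4 and a T1-T4 average should be made on what the trial is meant to estimate.

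**What to change.** In Section 14.1.2, state the response and its unit of analysis, and write for example: the primary model is a GEE for PD at T1-T4 with arm, visit, arm-by-visit, T0 PD and T0 PD-by-visit; the primary contrast is the Treatment-minus-Control difference at T4, with T1-T3 contrasts supportive. With T0 PD in the model, this difference equals the adjusted difference in change, so it agrees with Sections 1.2 and 14.2.

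In Section 14.2, add that the sample size was computed for the unadjusted T0-to-T4 change. If the sponsor prefers the T1-T4 average, keep the T0 terms and restate Section 14.2 for that contrast. If a separate plan already defines the model, cite it in Section 14.1.2.

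The T0 terms use four parameters (one main effect and three interactions). Section 8 sets the procedure: "Any changes to the protocol must be implemented only through formal written protocol amendments", with sponsor, investigator and IRB approval. No visits, samples or subjects are added.

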2.6. Randomization

Subjects are randomized to the Treatment or Control group at the Baseline (T0) visit following the protocol described in the Statistical Analysis Plan.

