14.1.3. Secondary Analyses

All secondary outcomes will be evaluated using the ITT population and GEE methodology. Systemic outcomes that are only applicable to a particular comorbid disease subgroup will only be evaluated in that population. Specifically, flow-mediated dilation and Carotid intima media thickness (IMT) will be evaluated in all subjects.

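### Does the second primary outcome need a written rule for claiming its two correlations?

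*Combined protocol and SAP*

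**What the plan says.** Section 1.2 lists two primary outcomes. The first is the effect of treatment on probing depth. The second is headed "Correlations between changes in periodontal health and changes in systemic health measures" and names HbA1c (prediabetes and type 2 diabetes cohorts) and FMD. The exploratory list in the same section contains "Correlations among all other oral and systemic health metrics".

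Section 14.1.2 gives the method for the second outcome: "The second primary outcome, association between changes in oral health and changes in systemic health, will be evaluated using correlation analysis". Changes run from T0 to T4, in everyone who completes T4. HbA1c is restricted to the diabetic and prediabetic subjects, and the sentence ends "or change in flow mediated dilation will be evaluated". No null hypothesis, significance level, order or success criterion is attached to either correlation.

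Section 14.2 sizes the trial on probing depth at a two-tailed 0.05: "we need 200 subjects (100 per group) to have 90% power to achieve statistical significance". It then tabulates the "effect sizes (i.e., Pearson correlation coefficients) this study would have the power to detect" for subgroups of one sixth to one half of 224 subjects. The alpha note under that table is truncated in the available text.

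A separate Statistical Analysis Plan is cited for randomization ("following the protocol described in the Statistical Analysis Plan", Section 2.6) and for exploratory details (Section 14.1.4). The available text contains no such separate plan.

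**The concern.** An outcome labelled primary is expected to come with a criterion for success. Here one outcome carries two correlations joined by an *or*, and Section 14.2 speaks of power, which has meaning only for a test. On that reading, a single significant correlation out of two could be presented as confirming the oral-systemic link, and the claim would carry nearly twice the conventional 5% error rate. Adding the probing-depth comparison makes three primary tests, each apparently at a full 0.05. Section 14.1.2 also refers only to oral health in general, so a reader might fear that the oral variable could be chosen after the data are seen, which would add further tests.

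**Working it through.** **1. The plan's own figures.**

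- Probing depth (inputs from Section 14.2): difference 0.88 − 0.63 = 0.25 mm, SDs 0.50 and 0.59. Pooled variance (0.25 + 0.3481)/2 = 0.299. Per group n = 2 × 0.299 × (1.960 + 1.282)² / 0.25² ≈ 101, against 100 stated. Power at 100 per group is about 90% (89.8% by the normal approximation, 89.6% by Welch). With 10% dropout, 100/0.9 ≈ 112. These agree with the plan.
- Correlation table, by Fisher's z: r = tanh[(z for alpha + z for power)/√(n − 3)]. The 80% power row:

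| Labelled N | 37 | 56 | 75 | 112 |
|---|---|---|---|---|
| Printed r | 0.468 | 0.386 | 0.336 | 0.277 |
| Two-sided 0.05, labelled N | 0.447 | 0.367 | 0.319 | 0.262 |
| Two-sided 0.025, labelled N | 0.484 | 0.400 | 0.348 | 0.287 |
| Two-sided 0.05, 90% of labelled N | 0.469 | 0.386 | 0.335 | 0.276 |

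The last line matches to 0.001, as it does in the 70% and 90% rows. The table was therefore probably computed at an unsplit two-sided 0.05 after 10% dropout. This is an inference, because the alpha note is incomplete.

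**2. The error rate if both are tested and either may be claimed.**

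- Two independent tests: 1 − 0.95² = 9.75%.
- Bound with no assumption on dependence: 0.05 + 0.05 = 10%.
- Jointly normal statistics: 9.51% at correlation 0.3, 9.07% at 0.5, 7.81% at 0.8.
- Simulation with 200 completers, assuming the HbA1c cohort is 50% or 75% of subjects and HbA1c and FMD changes correlate 0 to 0.8: 8.5–9.7% unadjusted, 4.4–4.9% with Holm.
- All three primary tests, any one claimed: 1 − 0.95³ = 14.3% if independent, and at most 15%.

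**3. What each way of closing the gap would cost.**

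- *Holm on the pair.* The smaller p-value is held to 0.025. Detectable r at 80% power, N = 100: from tanh(2.802/√97) = 0.277 to tanh(3.083/√97) = 0.303. At N = 200 (FMD in all subjects, an assumption for this analysis): from 0.197 to 0.216. A true r of 0.277 at N = 100 has 80% power at 0.05 and at least 71% under Holm. With probing depth at its own 0.05, the error across both primary outcomes can still reach 1 − 0.95 × 0.95 = 9.75%.
- *Probing depth first, then Holm.* This holds 5% overall, but the correlations become descriptive if probing depth fails.
- *Estimation only.* No alpha is spent and no significance claim is available. The 95% interval around r = 0 is about ±0.20 at N = 100 (tanh(1.96/√97) = 0.196) and ±0.14 at N = 200 (0.139).

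**4. Is the either-one rule in the plan?** Sections 1.2 and 14.1.2 name the two correlations and a method. Section 14.2 shows what size of correlation could be detected in cohorts of various sizes. Its largest column is half the study population, so it does not show power for FMD in the whole cohort. The statement that "flow-mediated dilation and Carotid intima media thickness (IMT) will be evaluated in all subjects" belongs to the secondary analyses. None of these sections says that one significant correlation is enough.

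**The case for a change.** The strongest case for a change is that the oral-systemic association is a primary claim, that a table of detectable correlations points to testing, and that this table fits a full 0.05 for each correlation. Dependence between the two systemic measures brings little relief: the simulated error stays at 8.5% or above even at correlation 0.8. A sentence would cost no subjects and leave probing-depth power untouched. Without it, a reader cannot tell whether one significant correlation of two was the planned criterion.

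Most of this stands as description. The arithmetic is right, and the available text has no claim rule. What does not follow is that the plan inflates an error rate. A planning table computed at 0.05 is not a decision rule, and Section 14.1.2 can be read just as well as estimation. The correlations pool completers from both groups, so they describe an association; the treatment effects on HbA1c and FMD are separate secondary outcomes. Multiplicity is also a usual subject of the Statistical Analysis Plan, so its absence from the protocol chapter is weak evidence that it was overlooked. As for the oral variable, probing depth is the primary oral measure, and correlations among the other metrics are placed in the exploratory list. Probing depth is the natural reading, though Section 14.1.2 does not say so outright.

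**Conclusion.** No change to the plan follows. The 9.75% (10% without a dependence assumption) is correct only if the correlations are formally tested, each is tested at 0.05, one alone may be claimed, and probing depth is the sole oral variable. The first and third conditions are not written anywhere in the available text, the second is inferred from a table, and the fourth is the natural reading. No stated error rate or power figure is shown to be wrong, and the sample size and the probing-depth comparison are unaffected.

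What remains is missing detail that a competent analyst fills sensibly: report both probing-depth correlations with 95% intervals, show both p-values if any are given, and do not present one of two as confirmation without saying so. A reader who sees both results can apply a 0.025 threshold unaided. Whether two correlations on distinct systemic endpoints need formal familywise control is a matter on which experienced statisticians differ, and every option has a price: about 9 points of power at r = 0.277 under Holm, dependence on probing depth under a fixed order, or no significance claim under estimation. This conclusion does not rely on the separate Statistical Analysis Plan containing a rule.
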